9. DATA COLLECTION

Data collection procedures on the affected extremity include psychometric assessments of pain, using the Numeric Pain Rating Scale and Visual Analogue Scale. Occupational performance will be measured using the Boston Carpal Tunnel Questionnaire completed by the participants and grip and pinch from each participant will be recorded by the student research assistants.

At the final visit, the student researcher and/or student research assistants will conduct a 30-minute 6-item semi-structured interview exploring the intervention group participant's perception of wearing Kinesio tape and its impact on the participant's occupational performance.

Study intervention will be held at the beginning of the week and the end of the week during various times of day to account for sign and symptoms related to occupation and activities of daily living. The researchers know which intervention is being studied; however, the participants will not know which intervention is being studied to increase accuracy of findings. The benefit of blinding participants in this graduate student randomized controlled trial to the objective of the study is to determine if there is indeed a benefit of the intervention of dorsal application of Kinesio Tape versus the usual protocol or current care of splint and lumbrical exercises for carpal tunnel syndrome forearm wrist hand pain. There Kinesio Tape application on the shoulder is to determine if there is an intervention effect is evidence to suggest even that application site could be beneficial. All participants will be emailed the results of the study.

Participants will complete a demographic questionnaire at baseline, which will include age, gender, ethnicity, current occupation and duration in that position. The demographic information will be used during data analysis to determine the influence of these variables on study outcomes. Participants will complete the Numeric Pain Rating Scale and Visual Analogue Scale to allow a subjective measure of participants experiencing mild to moderate carpal tunnel syndrome forearm wrist hand pain, which will be completed at baseline, weeks one, two, and three. These assessment tools are self-report measures using ordinal data with superior sensitivity, test retest reliability ($r = 0.96$ and 0.95) as well as construct validity ($r = 0.86$) (Hawker, Mian, Kendzerska, & French, 2011; Hjermstad et al., 2011). The student researcher and/or student research assistants at baseline will record functional grip at weeks one, two, and three using a calibrated Jamar Dynamometer and standardized protocol and position. The dynamometer is the only available tool to objectively measure functional grip

strength necessary to complete occupations of work, activities of daily living, household, and work tasks and demonstrates high test-retest reliability ($r > 0.80$), inter-rater reliability ($r = 0.98$) and concurrent validity (Roberts et al., 2011). Pinch strength will be collected by the student researcher or student research assistants at baseline, weeks one, two, and three using a calibrated pinch meter with standardized protocol and position as it is a commonly available tool to objectively measure functional pinch strength necessary for fine motor control, hand use for occupations and tasks of daily living skills. The pinch meter demonstrates high inter-rater reliability ($r = 0.97$) and test re-test reliability ($r = 0.80$) (Mathiowetz et al., 1985).

Participants will also complete an 11-question standardized Boston Carpal Tunnel Questionnaire a commonly accepted subjective measure of function and severity as it relates to carpal tunnel syndrome and efficacy related to functional activities using an ordinal scale. The Symptom Severity Scale demonstrates high test-retest reliability ($r = 0.91$), with internal consistency of 0.80 – 0.90, and the Functional Status Scale also demonstrates high test-retest reliability ($r = 0.93$) with internal consistency of 0.88 – 0.93 (Carvalho Leite, Jerosch-Herold, & Song, 2006).

See attached appendices D - O: Boston Carpal Tunnel Questionnaire, Demographic Questionnaire, Numeric Pain Rating Scale Questionnaire, Visual Analogue Scale, Splint and Exercise Compliance Log, Symptom Log, Kinesio Tape Removal Instructions, Interview Guide, Scripts.

10. LABELING & STORAGE OF DATA & SPECIMENS

Informed consents, HIPPA documents, and research records of functional grip and pinch measurements, occupational performance scales, and interviews will be stored in a locked cabinet in a locked office of the Principal Investigator. Any electronic research records of functional grip and pinch measurements, occupational performance scales, interviews and other research information will be stored on a secured and password protected computer. Data will be secured in a locked cabinet for a period of three years and then destroyed.

11. DATA ANALYSIS

The research analysis plan will include a repeated measures multi-factorial analysis of variance to analyze continuous data for the functional grip and pinch measurements, with an analysis of covariance to rule out any confounding variables between groups. For Objective 1 of the randomized controlled trial of the study continuous data will be analyzed with change score analysis from baseline to end of study. To compare groups post-hoc Bonferroni will be used. Non-parametric statistics using the Friedman's Test will be used with the Numeric Pain Rating Scale, Visual Analogue Scale, and Boston Carpal Tunnel Questionnaire.

For Objective 2, qualitative data will be analyzed for thematic coding. Transcripts will be individually read and coded for emerging themes by the research team and then analyzed as a group to increase rigor. For Objective 3 to explore concepts of adherence to interventions with carpal tunnel syndrome, triangulation will be used with data obtained through interviews and with journals using a deductive approach to explore Kinesio Tape on performance. Data will be analyzed until redundancy is achieved.

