6. SUBJECT RECRUITMENT & SCREENING

Based on a power analysis, 64 participants are needed with an expected attrition rate of 20% increasing the total number of participants to 78, with 26 in each of three groups.

Participants will be fluent in English, males and females age 18 years and older. The study will include participants from any race or ethnicity that meet eligibility criteria and demonstrate a positive Phalen's Test or positive Tinel's Test. The study population includes individuals who have symptoms of or have received a diagnosis of carpal tunnel syndrome, or experience forearm wrist hand pain and currently not receiving treatment. If participant has symptoms in both extremities, the researcher will use each extremity as a separate unit and apply corresponding intervention to both extremities.

Participants will be recruited using snowballing and judgmental sampling via word-of-mouth, flyers, emails, and social media with a \$5.00 gift card provided per visit for each of the five visits for the study. Flyers will be distributed throughout the Southern California area due to proximity but participants may come from any region if satisfying inclusion criteria and time commitment. Flyers will be placed in, but not limited to, common public places such as pet grooming places, community postings, manufacturing facilities, clinics, hair stylists, dental hygienists, sonographers, office buildings, and more. The principal investigator or appropriate personnel for Loma Linda University, and by the student researcher or appropriate personnel for the Stanbridge University access will acquire email addresses of potential participants. Specific social media outlets will include posting on but not limited to, Facebook, Instagram, and Twitter, with a website that will be accessed at: carpaltunnelstudy.wordpress.com for information. The contact information of the principal

investigator and student researcher will be available on the flyer with an invitation to contact researchers with any questions about the study.

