The primary purpose of this randomized controlled trial graduate student research study is to explore the effect of dorsal application of Kinesio Tape on occupational performance as measured by pain, strength, and function of individuals with carpal tunnel syndrome forearm wrist hand pain as compared to the usual and accepted most common non-surgical intervention of lumbrical stretching exercises and general cockup splint. The secondary purpose is to explore changes in occupational performance through semi-structured interviews in order to understand if Kinesio Tape contributed to results and if so, how. In order to help us understand how the participants perceived the interventions, the third purpose is to explore concepts of adherence to interventions with carpal tunnel syndrome.

b. Objectives

1. Determine if the dorsal application of Kinesio Tape applied to the wrist extensors for individuals with carpal tunnel syndrome and forearm wrist hand pain makes a difference in occupational performance as measured by pain, strength, and function.
2. Explore the perspectives of participants to understand if Kinesio Tape contributed to changes in occupational performance, and if so, how.

3. Explore concepts of adherence to interventions with carpal tunnel syndrome.

c. Procedures involved (Research Interventions)

The following procedures will be used for this multi-method study design that consists of a randomized control trial and descriptive qualitative study, upon IRB approval:

1. Recruit via snowballing, word-of-mouth, flyers, emails, and social media (See Appendix A)
2. Respond to study interest via Phone Script to answer questions regarding the study (See Appendix B) and set up a meeting time to review consent and initiate study procedures.
3. Review Informed Consent, HIPPA documents, and Patient's Bill of Rights and obtain consent from those interested in participating in study.
4. Screen participants for inclusion criteria by administering the Phalen's Test or Tinel's Test (Appendix C).
5. Administer Demographic questionnaire (Appendix D).
6. Administer baseline Week One Visit One Boston Carpal Tunnel Questionnaire, Numeric Pain Rating Scale, Visual Analogue Scale (Appendices E – F - G). If participant has symptoms in both extremities, the researcher will use each extremity as a separate unit and apply corresponding intervention to both extremities.
7. Collect Week One Visit One Baseline Grip and Pinch measurements (Appendix H).

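### The repeated-measures ANOVA for grip and pinch names no sphericity correction, covariance structure or missed-visit rule; uncorrected, its group-by-visit test would reject about 5% to 9% of the time at an assumed 5%

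*Combined protocol and SAP*

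**What the plan says.** Section 11 (Data Analysis) names as its first method a "repeated measures multi-factorial analysis of variance to analyze continuous data for the functional grip and pinch measurements", with an analysis of covariance for confounders. It then says that for Objective 1 "continuous data will be analyzed with change score analysis from baseline to end of study", and adds: "To compare groups post-hoc Bonferroni will be used". It gives no significance level, sphericity check, epsilon correction, multivariate test, covariance structure or rule for missed visits. It does not say which of the two analyses decides the strength question.

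Section 8c sets the schedule. Item 7 reads "Collect Week One Visit One Baseline Grip and Pinch measurements", and items 9 to 12 repeat the measurements at Visits Two to Five, with visits about three days apart in the first two weeks. Section 9 adds "Study intervention will be held at the beginning of the week and the end of the week". Its description of grip and pinch, however, lists baseline and weeks one, two and three, which read literally is four time points.

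Section 6 states "Based on a power analysis, 64 participants are needed", then an "expected attrition rate of 20% increasing the total number of participants to 78", "with 26 in each of three groups". Sections 6 and 8c also count the two hands of a bilateral participant as separate units, both given that participant's assigned intervention.

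**The concern.** The univariate repeated-measures F-test for within-person and group-by-visit effects is exact only under sphericity: the variance of the difference between any two visits must be the same. Measurements three days apart are usually more alike than measurements two weeks apart, which breaks that condition and makes the uncorrected p-values too small. Group-by-visit is the ANOVA term that asks whether the arms changed differently. If it is the term relied on, a false claim of differential change in strength becomes more likely than the nominal level suggests.

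The classical form of this ANOVA also needs every visit. Someone measured at baseline and Visit Five who missed one middle visit would be lost from it. Because the plan is silent, the version of the test and the handling of gaps could be chosen after the data are seen.

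**Working it through.** **The plan's own figure.** Sixty-four with 20% attrition gives 64 / (1 − 0.20) = 80, or 64 × 1.20 = 76.8, i.e. 77, which rounds up to 78 as a multiple of three. The stated 78 is therefore reproducible by the second route. The base of 64 cannot be checked, because alpha, power, effect size and test are not given.

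**Inputs from the documents.** Three arms of 26 (Section 6); five measurements (Section 8c), or four on a literal reading of Section 9. **Assumed, because not given:** a 5% level and the between-visit correlation pattern. Section 9 quotes test-retest reliability of above 0.80 for grip and 0.80 for pinch, but this does not fix how correlation falls with time.

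**The test.** Group-by-visit has (3 − 1)(5 − 1) = 8 and (78 − 3)(5 − 1) = 300 degrees of freedom. Departure from sphericity is measured by ε = [tr(CΣCᵀ)]² / {(k − 1) tr[(CΣCᵀ)²]}, where k is the number of visits, Σ the visit covariance and C orthonormal visit contrasts; ε = 1 under sphericity. Greenhouse-Geisser multiplies both degrees of freedom by the estimated ε. At ε = 0.689, for example, they become 8 × 0.689 = 5.5 and 300 × 0.689 = 206.7.

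**Rejection rates with no effect.** Simulation, 40,000 trials per setting (error about 0.1 point), 26 per arm, five visits, independent units:

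| Assumed pattern | ε | Uncorrected F | Greenhouse-Geisser |
|---|---|---|---|
| Compound symmetry, 0.8 | 1.00 | 5.0% | 4.5% |
| Serial 0.5 or 0.8, measurement error 50% of variance | 0.96 | 5.2% | 4.6% |
| Serial 0.5, measurement error 25% | 0.90 | 5.6% | 4.6% |
| Serial 0.8, measurement error 25% | 0.87 | 6.0% | 4.9% |
| Random slopes (three sizes) | 0.94 to 0.62 | 5.5% to 8.5% | 4.8% to 5.1% |
| AR(1) 0.3 | 0.92 | 5.5% | 4.7% |
| AR(1) 0.5 | 0.81 | 6.5% | 4.8% |
| AR(1) 0.6 | 0.75 | 7.0% | 5.0% |
| AR(1) 0.7 | 0.69 | 7.5% | 4.9% |
| AR(1) 0.8 | 0.63 | 8.4% | 5.1% |
| AR(1) 0.9 | 0.58 | 8.8% | 5.1% |
| AR(1) 0.95 | 0.55 | 9.0% | 5.1% |

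With arms of 21, 21 and 22 the AR(1) range is 5.5% to 9.2%. With four time points it is 5.4% to 7.8%.

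**Which alternatives control the error** (same settings, 26 per arm, five visits):
- A random-intercept mixed model gave the same F as the ANOVA in three simulated data sets (0.4339, 0.9503, 1.5742), so it corrects nothing.
- Unstructured covariance with a plain Wald chi-square test: 7.5% to 8.0%. With an F on naive within-subject degrees of freedom: 7.0% to 7.4%.
- Unstructured covariance with a small-sample F (McKeon): 4.8% to 5.2%. Kenward-Roger is a correction of the same kind but was not itself simulated.
- ANOVA with Huynh-Feldt: 4.9% to 5.3%.

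**Missed visits.** Attrition alone leaves 78 × 0.80 = 62.4. If a fraction m also misses each of Visits Two to Four (assumed), five-visit cases number 62.4 × (1 − m)³. For m = 2% this is 62.4 × 0.941 = 58.7; for m = 5% it is 62.4 × 0.857 = 53.5. The further loss is about 4 to 9 cases.

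**Paired hands.** An illustrative run took AR(1) 0.7, 30% to 50% of participants bilateral and between-hand correlation 0.3 to 0.7 (4,000 trials each, all assumed). Treating hands as independent, the uncorrected F rejects 12.6% to 23.7%, Greenhouse-Geisser 8.2% to 18.2%, and the unstructured small-sample test 9.8% to 22.8%. With no bilateral participants the same run gives 8.6%, 5.4% and 5.5%.

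**The case against.** The strongest reply is that the analysis tied by name to Objective 1 is the change score. It uses one value per unit, so sphericity does not arise, and a missed middle visit removes nobody. That stands, and it limits what is at stake. It does not dispose of the point, because the ANOVA remains a planned test of strength and the plan does not rank the two.

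Second, the plan does not say the F-test will be uncorrected; Greenhouse-Geisser, Huynh-Feldt and multivariate versions are all repeated-measures ANOVA. A reader might infer that the reported p-values will be too small. The documents support only that the version is unspecified.

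Third, a reader might take 7% to 9% as the error rate. That needs serial correlation of about 0.6 or more with no measurement error, at a level the plan does not state. The reliabilities quoted in Section 9 are imperfect, which points towards some measurement error and hence a smaller excess. The range has to be given as about 5% to 9%.

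Fourth, replacing the ANOVA is not needed to cure sphericity, since Greenhouse-Geisser does so. This is also right. The case for the mixed model rests as well on its use of all available visits. The 2% to 5% missed-visit rates have no source in the documents, so the size of that loss is illustrative only.

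**Conclusion.** The point holds as a cheap and worthwhile improvement. The grip and pinch ANOVA is under-specified. If run uncorrected at an assumed 5%, its group-by-visit test rejects between 5% and about 9% of the time, depending on an unstated correlation pattern; with four time points the AR(1) maximum is 7.8%. In its classical form it would also drop participants with any missed visit. The change-score analysis is untouched by sphericity.

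A tempting stronger reading is that any mixed model would remove the problem. It would not: a random intercept alone reproduces the ANOVA F, and plain Wald tests still reject about 7.5% to 8.0%. Nor would a model for visits alone restore 5% under this protocol, because paired hands are counted as independent units. Under the illustrative assumptions that is the larger source of error.

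**What to change.** Analyse grip and pinch each with a linear mixed model containing arm, visit and arm-by-visit, unstructured covariance across visits, Kenward-Roger degrees of freedom and all available visits. Take the between-arm contrast at Visit Five from this model. Add a participant-level effect for bilateral participants. It should let the two hands share changes over time (participant-by-visit), because a constant participant intercept cancels out of visit-to-visit contrasts.

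If the ANOVA is kept, base every within-person and interaction p-value on Greenhouse-Geisser, and use one value per participant or another stated allowance for paired hands.

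In either case, state the significance level, say whether the ANOVA (or its replacement) or the change score decides, reconcile the five visits of Section 8c with the four time points of Section 9, and say how missed visits are handled.

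The cost is plan wording, a few lines of code and a little more analysis work; interaction p-values become slightly less favourable. Visits and sample size do not change.

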9. Week One Visit Two a student researcher and/or student research assistants will remove Kinesio Tape, check splints, and collect symptom journals and the Usual protocol group Splint-wearing and Exercise journal. Participants will complete Boston Carpal Tunnel Questionnaire, Numeric Pain Rating Scale, Visual Analogue Scale. Grip and Pinch measurements will be recorded.

Student researcher and/or student research assistants will re-apply Kinesio Tape and check splint and exercises resumed with the Usual protocol group.

Total exposure to application and removal of Kinesio Tape is four times as participants return every third day of Weeks One and Two.

10. Week Two Visit Three a student researcher and/or student research assistants will remove Kinesio Tape, check splints, and collect symptom journals and the Usual protocol group Splint-wearing and Exercise journal. Participants will complete Boston Carpal Tunnel Questionnaire, Numeric Pain Rating Scale, Visual Analogue Scale. Grip and Pinch measurements will be recorded.

Student researcher and/or student research assistants will re-apply Kinesio Tape and check splint and exercises resumed with the Usual protocol group.

11. Week Two Visit Four a student researcher and/or student research assistants will remove Kinesio Tape, check splints, and collect symptom journals and the Usual

protocol group Splint-wearing and Exercise journal. Participants will complete Boston Carpal Tunnel Questionnaire, Numeric Pain Rating Scale, Visual Analogue Scale. Grip and Pinch measurements will be recorded.

Student researcher and/or student research assistants will re-apply Kinesio Tape and check splint and exercises resumed with the Accepted protocol group.

12. Week Three Visit Five a student researcher and/or student research assistants will remove Kinesio Tape, check splints, and collect symptom journals and the Usual protocol group Splint-wearing and Exercise journal. Participants will complete Boston Carpal Tunnel Questionnaire, Numeric Pain Rating Scale, Visual Analogue Scale. Grip and Pinch measurements will be recorded.
13. Up to 26 participants from the Intervention group will be invited to participate in a 30-minute semi-structured audio-recorded interview with student researcher (Appendix N).
14. Email Reminder Script regarding study date (Appendix O)
15. See Timeline (Appendix P)

- d. Concise review of literature that supports the rationale, objectives, and methodology of the proposed study.

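### Objective 1 for grip and pinch is answered by a baseline-to-end change score; adjusting for the baseline strength already collected, which the plan does not name as a covariate, would be modestly more precise

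*Combined protocol and SAP*

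**What the plan says.** Section 11 (Data Analysis) mentions three analyses for the continuous outcomes, grip and pinch:

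- a repeated-measures ANOVA with several factors;
- alongside it, "with an analysis of covariance to rule out any confounding variables between groups";
- for Objective 1, "continuous data will be analyzed with change score analysis from baseline to end of study", with Bonferroni-corrected group comparisons.

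The ANCOVA covariates are not listed. The only variables that the documents tie to the analysis are demographic: section 9 (Data Collection) says "The demographic information will be used during data analysis to determine the influence of these variables on study outcomes".

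Baseline strength is measured. Step 7 of the procedures in section 8 reads "Collect Week One Visit One Baseline Grip and Pinch measurements", and random assignment is step 8. The entries for Visits 2 to 5 each state "Grip and Pinch measurements will be recorded".

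Section 6 plans 26 participants in each of three groups, expects 20% attrition, and treats each affected hand of a participant with symptoms on both sides as a separate unit. The text does not say how early leavers enter the strength analysis.

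**The concern.** A change score subtracts the whole baseline value. Unless baseline and final values are almost perfectly correlated, that removes too much and carries baseline noise into the outcome. Regressing the final value on baseline estimates how much to remove. Both target the same treatment contrast under randomisation, so choosing the change score gives up precision and saves nothing, because the baseline is in hand. With about 21 completers per group, even a modest loss is worth avoiding.

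A change from first to last visit also cannot be computed without a last visit. Strength recorded at Visits 2-4 in participants who then leave would add nothing to that analysis.

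Finally, three analyses of the same data with no stated order leave open which one answers Objective 1 and whether baseline strength is adjusted for in any of them.

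**Working it through.** **The plan's own figures.** The plan gives no figure for the precision of the strength analysis. Its only related numbers are the sample size: 64, raised to 78 for 20% attrition. The 64 cannot be reproduced, because no effect size, standard deviation, error rate or power is given. For the increase, 64 x 1.2 = 76.8, which becomes 78 in three equal groups; 64 / 0.8 would give 80. Completers: 26 x 0.8 = 20.8 per group, 78 x 0.8 = 62.4 in all.

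**Assumption.** Let r be the within-group correlation of baseline with Visit 5 strength, taking Visit 5, the last scheduled visit, as end of study. The documents do not give r. Section 9 cites test-retest reliability above 0.80 for grip and of 0.80 for pinch. That is a different quantity and only a guide, so a range is shown.

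**Complete data, equal standard deviation s at both times.**

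- Change score: variance = 2(1 - r)s².
- Baseline-adjusted: variance = (1 - r²)s².
- Ratio = (1 + r)/2.
- Cost of estimating the slope with three groups: multiply by 1 + 1/(N - 5), which is 1 + 1/57 = 1.0175 at N = 62 and 1 + 1/73 = 1.0137 at N = 78.

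| r | Large-sample ratio | N = 78 | N = 62 | Variance saved |
|---|---|---|---|---|
| 0.5 | 0.75 | 0.760 | 0.763 | about 23-25% |
| 0.8 | 0.90 | 0.912 | 0.916 | about 8-10% |
| 0.9 | 0.95 | 0.963 | 0.967 | about 3-5% |

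Simulation at r = 0.8 agrees: 0.909 with 26 per group and 0.916 with 21. On the standard-error scale, √0.90 = 0.949 and √0.916 = 0.957, so 4-5% smaller. A two-group contrast with 80% power on change scores would have about 83-84% with adjustment.

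If the two standard deviations differ (s0 at baseline, s1 at the end), the large-sample difference is s0² + s1² - 2r·s0·s1 - s1²(1 - r²) = (s0 - r·s1)². This is never negative. With equal standard deviations and N = 62, the slope cost cancels the gain only when (1 + r)/2 = 57/58, that is r = 56/58, about 0.97.

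**With 20% random dropout.** Simulated inputs: 3 x 26 participants, one hand each, five visits, dropout spread evenly after Visits 1-4, and correlation either equal between all visits (exchangeable) or decaying so that Visits 1 and 5 correlate r. Standard error of the tape-control contrast at Visit 5, in SD units:

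| r | Correlation | Change score | ANCOVA, completers | Longitudinal model |
|---|---|---|---|---|
| 0.5 | exchangeable | 0.309 | 0.271 | 0.268 |
| 0.5 | decaying | 0.313 | 0.273 | 0.264 |
| 0.8 | exchangeable | 0.198 | 0.189 | 0.185 |
| 0.8 | decaying | 0.198 | 0.190 | 0.183 |
| 0.9 | exchangeable | 0.141 | 0.138 | 0.135 |
| 0.9 | decaying | 0.139 | 0.136 | 0.131 |

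At r = 0.8 the ANCOVA cuts variance by about 8% (ratio 0.92) and the longitudinal model by 12-15% (ratios 0.877 and 0.852).

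**Dropout that depends on response (illustration only).** The dropout rules and the true effect of 0.50 SD are assumed; r = 0.8, with results given as exchangeable, decaying.

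- Poor observed change drives leaving, tape group only: change score 0.56, 0.57; ANCOVA 0.55, 0.57; model 0.50, 0.50.
- The same rule in all groups: change score 0.48, 0.47; ANCOVA 0.48, 0.47; model 0.50, 0.50.
- Leaving depends on the unobserved Visit 5 change: the model removes only about 27-45% of the change-score bias.

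So the ANCOVA alone leaves dropout bias almost where it was.

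**The case against.** The strongest reply is that section 11 already plans an ANCOVA. A reader might infer from the Objective 1 sentence that the plan has no baseline adjustment at all. The documents do not support that: the covariates are unlisted, so baseline strength is unnamed, not excluded. If it enters that ANCOVA, the complete-data gain is already obtained there. What remains is that the analysis assigned to Objective 1 is the change score, and nothing links it to the ANCOVA.

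Second, the gain is modest and rests on an r that the documents do not supply. If r for grip really exceeds 0.8, the saving is below the figures for 0.8. This stands, and it makes the point one of efficiency and pre-specification.

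A reader might go further and call the change score biased, or say that the plan discards early leavers. Neither is shown. With complete data the change score is unbiased under randomisation. The text is silent on early leavers, and the repeated-measures ANOVA may take in the intermediate visits, although a standard version can also drop incomplete cases. The direction and size of any dropout bias cannot be read from the documents.

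A reader might also see a conflict between weekly strength measurement in section 9 and the visits in section 8. There is none: Visits 2-5 fall in weeks one, two and three.

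Last, the longitudinal model is more demanding for a small student trial. That is fair, and is why the simpler ANCOVA is offered as the minimum.

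**Conclusion.** The point holds as a modest improvement in precision and clarity. For strength, the Objective 1 analysis is a change score where a baseline-adjusted analysis of the same data would do better: about 8-10% less variance at an assumed r = 0.8, 23-25% at 0.5 and 3-5% at 0.9. These figures assume complete data, equal standard deviations and one hand per participant; bilateral participants were not examined. The further gain from the longitudinal model (12-15% in total at r = 0.8) also assumes 20% random dropout.

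The point concerns grip and pinch only. No primary outcome is named, so it is not shown to drive the trial's main conclusion.

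**What to change.** **Minimum.** Replace the change score with an ANCOVA on Visit 5 strength adjusted for baseline strength, separately for grip and pinch. Account for two hands from one participant, for example with a participant-level random effect or cluster-robust standard errors. State that this analysis answers Objective 1 for strength, and what role the repeated-measures ANOVA then has. Name any other covariates in advance.

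**Preferred.** Fit one longitudinal model each for grip and pinch, with Visits 2-5 as outcomes and group, visit, group-by-visit, baseline and baseline-by-visit as fixed effects. Use an unstructured covariance across visits, with a simpler structure named in advance if it does not converge, and the same allowance for two hands. Take the Visit 5 group contrasts with the planned Bonferroni correction. State that the model assumes data are missing at random, only partly protects when leaving depends on unobserved values, and gains nothing from participants with no follow-up visit.

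**Cost.** Wording only: baseline and all four follow-up measurements are already scheduled. The ANCOVA is about as simple as the analysis it replaces. The longitudinal model is slightly more complex in a small trial and needs the stated fallback.
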